## **6 Adverse Events**

Adverse events will be recorded in the medical record at each visit from the time the patient receives the first dose of study drug. The first dose of study drug includes all three drugs (methylprednisolone, ofatumumab, and lenalidomide). Adverse event data entry will be captured in the Oncore database on day 1 of each cycle. The NCI CTCAE v4.0 (see Appendix G) will be used as a guide for the grading of adverse event severity.

All adverse events will be followed for 30 days after the last dose in cycle 12 of study treatment, unless the subject withdraws consent, or begins other CLL treatment.

If a subject completes all 12 cycles of the protocol therapy and enters lenalidomide Maintenance Therapy (MT), any unresolved adverse events will be considered ongoing. In MT, only grade 3 or 4 cytopenias will be captured as adverse events and recorded in Oncore.

## **6.1 Serious adverse event reporting to Celgene Corporation**

Celgene Corporation must be notified according to Celgene serious adverse event (SAE) definition. A serious adverse event is one that at any dose (including overdose):

- Results in death
- Is life-threatening
- Requires inpatient hospitalization or prolongation of existing hospitalization
- Results in persistent or significant disability or incapacity
- Is a congenital anomaly or birth defect
- Is an important medical event
- Pregnancy

“Life-threatening” means that the subject was at immediate risk of death at the time of the serious adverse event; it does not refer to a serious adverse event that hypothetically might have caused death if it were more severe.

“Persistent or significant disability or incapacity” means that there is a substantial disruption of a person’s ability to carry out normal life functions.

Medical and scientific judgment should be exercised in deciding whether expedited reporting is appropriate in situations where none of the outcomes listed above occurred. Important medical events that may not be immediately life-threatening or result in death or hospitalization but may jeopardize the patient or may require intervention to prevent one of the other outcomes listed in the definition above should also usually be considered serious. Examples of such events include allergic bronchospasm requiring intensive treatment in an emergency room or at home, blood dyscrasias or convulsions that do not result in inpatient hospitalization, or the development of drug dependency or drug abuse. A new diagnosis of cancer during the course of a treatment should be considered as medically important.

### **6.1.1 Adverse Event Reporting**

Toxicity will be scored using CTCAE Version 4.0 for toxicity and adverse event reporting. A copy of the CTCAE Version 4.0 can be downloaded from the CTEP homepage (<HTTP://CTEP.INFO.NIH.GOV>). All appropriate treatment areas should have access to a copy of the CTCAE Version 4.0. All adverse clinical experiences, whether observed by the investigator or reported by the patient, must be recorded, with details about the duration and intensity of each episode, the action taken with respect to Amendment 5 Dated 03/02/2016

---

the test drug, and the patient's outcome. The investigator must evaluate each adverse experience for its relationship to the test drug and for its seriousness.

The investigator must appraise all abnormal laboratory results for their clinical significance. If any abnormal laboratory result is considered clinically significant, the investigator must provide details about the action taken with respect to the test drug and about the patient's outcome.

#### **6.1.2 Pregnancies**

Pregnancy of a female subject or the female partner of a male subject occurring while the subject is on lenalidomide or within 4 weeks after the subject's last dose of lenalidomide are considered expedited reportable events. If the subject is on lenalidomide, it is to be discontinued immediately and the subject is to be instructed to return any unused portion of lenalidomide to the Investigator. The pregnancy must be reported to Celgene and Novartis Drug Safety within 24 hours of the Investigator's knowledge of the pregnancy by phone and facsimile using the SAE Form.

The Investigator will follow the pregnant female until completion of the pregnancy, and must notify Celgene and Novartis Drug Safety of the outcome as specified below. The Investigator will provide this information as a follow-up to the initial SAE.

If the outcome of the pregnancy meets the criteria for immediate classification as a SAE (i.e., spontaneous abortion [any congenital anomaly detected in an aborted fetus is to be documented], stillbirth, neonatal death, or congenital anomaly), the Investigator should follow the procedures for Expedited Reporting of SAEs to Celgene and Novartis (i.e., report the event to Celgene and Novartis Drug Safety by facsimile within 24 hours of the Investigator's knowledge of the event).

Any suspected fetal exposure to lenalidomide must be reported to Celgene and Novartis within 24 hours of being made aware of the event. The pregnant female should be

Amendment 5 Dated 03/02/2016

---

referred to an obstetrician/gynecologist experienced in reproductive toxicity for further evaluation and counseling.

All neonatal deaths that occur within 30 days of birth should be reported, without regard to causality, as SAEs. In addition, any infant death after 30 days that the Investigator suspects is related to the *in utero* exposure to lenalidomide should also be reported.

In the case of a live “normal” birth, Celgene and Novartis Drug Safety should be advised as soon as the information is available.

#### **6.1.4 Investigator Reporting Responsibilities**

The conduct of the study will comply with all FDA safety reporting requirements.

##### IND Annual Reports

If the FDA has granted an IND number, it is a requirement of 21 CFR 312.33, that an annual report is provided to the FDA within 60-days of the IND anniversary date. 21 CFR 312.33 provides the data elements that are to be submitted in the report. The

---

Annual Report should be filed in the study's Regulatory Binder, and a copy provided to Celgene Corporation as a supporter of this study as follows.

Celgene Corporation  
Attn: Medical Development  
[name]  
[name]  
[contact]

All adverse experience reports must include the patient number, age, sex, weight, severity of reaction (e.g. mild, moderate, severe), relationship to drug (e.g. probably related, unknown relationship, definitely not related), date and time of administration of test medications and all concomitant medications, and medical treatment provided. The investigator is responsible for evaluating all adverse events to determine whether criteria for "serious" and as defined above are present. The investigator is responsible for reporting adverse events to Celgene as described below.

#### **6.1.5 Expedited reporting by investigator to Celgene**

Serious adverse events (SAE) are defined above. The investigator must inform Celgene in writing using a Celgene SAE form or MEDWATCH 3500A form of any SAE within 24 hours of being aware of the event. The written report must be completed and supplied to Celgene by facsimile within 24 hours/1 business day. The initial report must be as complete as possible, including an assessment of the causal relationship between the event and the investigational product(s), if available. Information not available at the time of the initial report (e.g., an end date for the adverse event or laboratory values received after the report) must be documented on a follow-up report. A final report to document resolution of the SAE is required. The Celgene tracking number (RV-CLL-PI-0560) and the institutional protocol number should be included on SAE reports (or on the fax cover letter) sent to Celgene. A copy of the fax transmission confirmation of the SAE report to Celgene should be attached to the SAE and retained with the patient records.

Amendment 5 Dated 03/02/2016

## **6.2 Serious Adverse Event Reporting to Novartis**

NOVARTIS must be informed according to NOVARTIS Serious Adverse Event Definitions.

### **Adverse Events:**

Any untoward medical occurrence in a subject or clinical investigation subject, temporally associated with the use of a medicinal product, whether or not considered related to the medicinal product.

Events meeting the definition of an AE include:

- Any abnormal laboratory test results (hematology, clinical chemistry, or urinalysis) or other safety assessments e.g., ECGs, radiological scans, vital signs measurements), including those that worsen from baseline, and felt to be clinically significant in the medical and scientific judgment of the investigator
- Exacerbation of a chronic or intermittent pre-existing condition including either an increase in frequency and/or intensity of the condition
- New conditions detected or diagnosed after investigational product administration even though it may have been present prior to the start of the study
- Signs, symptoms, or the clinical sequelae of a suspected interaction
- Signs, symptoms, or the clinical sequelae of a suspected overdose of either investigational product or a concomitant medication (overdose per se will not be reported as an AE/SAE)

“Lack of efficacy” or “failure of expected pharmacological action” per se will not be reported as an AE or SAE. However, the signs and symptoms and/or clinical sequelae resulting from lack of efficacy will be reported if they fulfill the definition of an AE or SAE.

Events that **do not** meet the definition of an AE include:

Amendment 5 Dated 03/02/2016

---

- Any clinically significant abnormal laboratory finding or other abnormal safety assessments that is associated with the underlying disease, unless judged by the investigator to be more severe than expected for the subject's condition.
- The disease/disorder being studied, or expected progression, signs, or symptoms of the disease/disorder being studied, unless more severe than expected for the subject's condition
- Medical or surgical procedure (e.g., endoscopy, appendectomy); the condition that leads to the procedure is an AE
- Situations where an untoward medical occurrence did not occur (social and/or convenience admission to a hospital)
- Anticipated day-to-day fluctuations of pre-existing disease(s) or condition(s) present or detected at the start of the study that do not worsen
- B cell depletion and hypogammaglobulinemia due to ofatumumab treatment

#### **6.2.1 Definition of a Serious Adverse Event (SAE)**

An SAE is an Adverse Event that, at any dose:

- a. Results in death
- b. Is life-threatening

NOTE: The term 'life-threatening' in the definition of 'serious' refers to an event in which the subject was at risk of death at the time of the event. It does not refer to an event, which hypothetically might have caused death, if it were more severe.

- c. Requires hospitalization or prolongation of existing hospitalization

NOTE: In general, hospitalization signifies that the subject has been detained (usually involving at least an overnight stay) at the hospital or emergency ward for observation and/or treatment that would not have been appropriate in the physician's office or out-patient setting. Complications that occur during hospitalization are AEs. If a complication prolongs hospitalization or fulfills any other serious criteria, Amendment 5 Dated 03/02/2016

---

the event is serious. When in doubt as to whether “hospitalization” occurred or was necessary, the AE should be considered serious.

Hospitalization for elective treatment of a pre-existing condition that did not worsen from baseline is not considered an AE.

An overnight hospital stay due to slow infusion rates will not be considered a Serious Adverse Event.

d. Results in disability/incapacity, or

NOTE: The term disability means a substantial disruption of a person's ability to conduct normal life functions. This definition is not intended to include experiences of relatively minor medical significance such as uncomplicated headache, nausea, vomiting, diarrhea, influenza, and accidental trauma (e.g. sprained ankle) which may interfere or prevent everyday life functions but do not constitute a substantial disruption.

e. Is a congenital anomaly/birth defect

f. Medical or scientific judgment should be exercised in deciding whether reporting is appropriate in other situations, such as important medical events that may not be immediately life-threatening or result in death or hospitalization but may jeopardize the subject or may require medical or surgical intervention to prevent one of the other outcomes listed in the above definition. These should also be considered serious. Examples of such events are invasive or malignant cancers, intensive treatment in an emergency room or at home for allergic bronchospasm, blood dyscrasias or convulsions that do not result in hospitalization, or development of drug dependency or drug abuse.

#### **6.2.2 Laboratory and Other Safety Assessment Abnormalities Reported as AEs and SAEs**

- Any abnormal laboratory test results (hematology, clinical chemistry, or urinalysis) or other safety assessments (e.g., ECGs, radiological scans, vital signs

measurements), including those that worsen from baseline, and felt to be clinically significant in the medical and scientific judgment of the investigator **are** to be recorded as AEs or SAEs.

- All events meeting liver stopping criteria must be recorded as an SAE.
- However, any clinically significant safety assessments that are associated with the underlying disease, unless judged by the investigator to be more severe than expected for the subject's condition, are **not** to be reported as AEs or SAEs.
- B cell depletion, IgG below LLN, low CD19+ count, and hypogammaglobulinemia due to treatment with ofatumumab are **not** to be reported as AEs or SAEs.
- Infusion related AEs may lead to a prolonged infusion time. Overnight stay at the hospital due to slow infusion rate is **not** to be reported as a SAE.

#### **6.2.3 Disease-Related Events and/or Disease-Related Outcomes Not Qualifying as SAEs**

An event which is part of the natural course of the disease under study (i.e., disease progression) does not need to be reported as an SAE. However, if the progression of the underlying disease is greater than that which would normally be expected for the subject, or if the investigator considers that there was a causal relationship between treatment with investigational product or protocol design/procedures and the disease progression, then this must be reported as an SAE.

#### **6.2.4 Time Period and Frequency of Detecting and SAEs**

Once an investigator determines that an event meets the protocol definition of an SAE, the SAE will be reported to Novartis within 24 hours of being notified of the event. All SAEs regardless of relationship to investigational product will be collected from the first dose of investigational product to after the last dose of investigational product (minimum of 6 months or until the end of the follow-up period which ever is longer). All SAEs regardless of causality will be collected until the end of the follow-up period.

Amendment 5 Dated 03/02/2016

---

From the time a subject consents to participate in and completes the study all SAEs assessed as related to study participation (e.g., protocol-mandated procedures, invasive tests, or change in existing therapy) or related to NOVARTIS concomitant medication, will be reported promptly to NOVARTIS.

Any SAE brought to the investigator's attention after the subject has completed the study and considered by the investigator as possibly related to investigational product must be reported to NOVARTIS.

This includes serious, related, not related, labeled (expected) and, unlabeled (unexpected) adverse experiences. All deaths during treatment or within 30 days following completion of active protocol therapy must be reported within 24 hours.

Any SAEs experienced after the follow-up period should only be reported to Novartis if the investigator suspects a causal relationship to the study drug. Recurrent episodes, complications, or progression of the initial SAE must be reported as follow-up to the original episode within 24 hours of the investigator receiving the follow-up information. A SAE occurring at a different time interval or otherwise considered completely unrelated to a previously reported one should be reported separately as a new event. The end date of the first event must be provided.

The original copy of the SAE Report and the fax confirmation sheet must be kept within the Trial Master File at the study site.

Follow-up information is sent to the same fax number as the original SAE Report Form was sent, using a new fax cover sheet, stating that this is a follow-up to the previously reported SAE, and giving the date of the original report. Each re-occurrence, complication, or progression of the original event should be reported as a follow-up to that event regardless of when it occurs. The follow-up information should describe whether the event has resolved or continues, if and how it was treated and whether the patient continued or withdrew from study participation.

If the SAE is not previously documented in the Ofatumumab Investigator Brochure or Package Insert (new occurrence) and is thought to be related to the Novartis study drug, a DS&E associate may urgently require further information from the investigator for Health Authority reporting. Novartis may need to issue an Investigator Notification (IN), to inform all investigators involved in any study with the same drug that this SAE has

Amendment 5 Dated 03/02/2016

---

been reported. Suspected Unexpected Serious Adverse Reactions (SUSARs) will be collected and reported to the competent authorities and relevant ethics committees in accordance with Directive 2001/20/EC or as per national regulatory requirements.

For medical emergencies, the contact is:

[name] MD  
Medical Director  
US CD MA Hematology  
Novartis Pharmaceuticals Corporation  
[name]  
[name]  
[contact]  
[[contact]](mailto:[contact])

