## 2 Schedule of Study Assessments \*

Procedure	All visits/assessments may be scheduled $\pm$ 3 business days										
	Screening  <math>\leq</math> 28 days from Baseline (First day drug administration)	Cycle 1	Cycles 2 - 3	Cycle 4 				Cycles 5-12	Lenalidomide Maintenance Therapy	Discontinuation From Protocol Therapy 	Follow- Up Phase
	Days 1, 8, 15, and 22	Days 1, and 15	Day 1	Day 3 or 4 at investigator discretion	Day 8	Day 15	Day 22	Day 1 and 15			
Study drug administration **		X	X	X					X	X	
Record prior medications, treatments	X										
Record prior anti-cancer therapies	X										
Physical examination, vital signs, weight	X	X 	X 	X 					X 		
ECOG performance status	X	X 	X 	X 					X 		
ECG	X										
Assess lymphadenopathy, spleen / liver 		X 	X 	X 		X 	X 		X 		
Peripheral blood for , ZAP 70, $\beta$ -2 microglobulin, and IgHV mutational status 	X										
Research samples 	X			X							
Baseline lesion assessment	X			X							
Bone marrow 	X			X					X	X	X 
CT of the neck, chest, abdomen & pelvis 	X			X					X		X 
Hematology 	X	X	X	X 		X 	X 	X 	X 	X 	
Serum chemistry 	X	X	X	X 	X 	X 	X 	X 	X 	X 	
Hepatitis B and C serology, HBV DNA PCR 	X 										
Pregnancy testing 	X			X		X	X	X	X		
Register patient into REMS® program	X										

Prescribe lenalidomide via REMS 				X				X			
Record adverse events 		X	X	X				X	X 		
Record concomitant therapies/procedures		X	X	X				X			
Obtain Follow-Up anti-cancer treatments											X
Obtain Follow-Up survival information											X

\* An unscheduled visit can occur at any time during the study. Source must be maintained for these unscheduled visits. The date for the visit and any data generated must be recorded on the appropriate CRF. Source documents for these unscheduled visits must also be maintained.

\*\* See Table 1 for detailed study drug administration schedule.

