 Pregnancy test for females of childbearing potential. A female of childbearing potential (FCBP) is a sexually mature female who: 1) has not undergone a hysterectomy or bilateral oophorectomy; or 2) has not been naturally postmenopausal for at least 24 consecutive months (i.e., has had menses at any time in the preceding 24 consecutive months). Pregnancy tests must occur within 10 – 14 days and again within 24 hours prior to prescribing lenalidomide for Cycle 1 (prescriptions must be filled within 7 days). FCBP with regular or no menstruation must have a pregnancy test weekly for the first 28 days and then every 28 days while on lenalidomide therapy (including breaks in therapy); at discontinuation of lenalidomide and at Day 28 post the last dose of lenalidomide. Females with irregular menstruation must have a pregnancy test weekly for the first 28 days and then every 14 days while on lenalidomide therapy (including breaks in therapy), at discontinuation of lenalidomide and at Day 14 and Day 28 post the last dose of lenalidomide (see Appendix: Risks of Fetal Exposure, Pregnancy Testing Guidelines and Acceptable Birth Control Methods).

 Adverse event data entry will be captured on day 1 of each cycle. An additional safety assessment will be done 28 days (+/- 2 days) following the last dose of protocol therapy.

 If physical examination, vital signs, weight and ECOG performance status were done within 7 days of Day 1, they do not need to be repeated on Day 1. During cycle 1 the physical examination will be done on day 1 and day 15. On subsequent cycles it will be done on day 1 only.

 Lenalidomide must be prescribed through and in compliance with the REMS® program of Celgene Corporation. Prescriptions must be filled within 7 days. Consideration should be given to prescribing lenalidomide 5 to 7 days in advance of Day 1 of each cycle to allow time for required patient and prescriber surveys, and drug shipment to patient. Any unused Revlimid® (lenalidomide) should be returned to the patient for disposition in accordance with the REMS® program.

 Any required screening tests that have been performed as standard of care prior to consent and are within 28 days of starting study treatment may be used for screening and do not need to be repeated. A bone marrow biopsy performed within 6 weeks of starting study treatment does not need to be repeated during screening.

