#### **5.4 Visit schedule and assessments**

Screening Assessments and all on study scheduled visits and assessments are outlined in Section 2: Table of Study Assessments.

Research samples for storage will be drawn during screening, day 1 of cycle 4, day 1 of Maintenance Therapy (or at time of discontinuation therapy if earlier than cycle 12). At each timepoint the following tubes will be obtained: three 10 ml green tops and one 10 ml

Amendment 5 Dated 03/02/2016

---

plain red top tube. The samples will be stored in the Moffitt Cancer Center laboratory of [name] for examining sample phenotypics and analysis of functionality of T-cell sub-populations. At treatment discontinuation, subjects will undergo off study evaluations per the Schedule of Assessments, Section 2. Study subjects who have completed the 12 cycles of treatment protocol, have not progressed while on therapy, and do not continue on lenalidomide maintenance therapy (MT) will be followed every 6 months for survival until disease progression, study closure, withdrawal of consent, or death. Subjects who progress while on MT and discontinue treatment will do the end of treatment testing. If the bone marrow biopsy and CT scans have been performed in the past 28 days to determine progression of disease, it is not necessary to repeat these tests.

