**5.7 Discontinuation of Study Treatment (See Also Section 5.5.3.5 and 5.5.3.6)**

Treatment will continue as per dosing schema. Treatment will be discontinued at the occurrence of any of the following events.

- Disease progression
- Adverse event(s) that, in the judgment of the Investigator, may cause severe or permanent harm or which rule out continuation of the treatment regimen.
- Discontinuation of treatment protocol for any reason.
- Major violation of the study protocol.
- Withdrawal of consent
- Lost to follow up

---

- Death
- Pregnancy or a positive pregnancy test

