### **5.9 Follow-Up**

If a subject discontinues study treatment at any time during cycles 1-12, “Discontinuation from Protocol Therapy” on the Schedule of Assessments, Section 2 will be performed. If the bone marrow biopsy and CT scans have been performed in the past 28 days to determine progression of disease, it is not necessary to repeat them.

The subject will then enter the follow-up period unless consent is withdrawn. If a subject enters Maintenance Therapy (MT) after cycle 12, the follow-up period will begin after discontinuation of lenalidomide in MT. If a subject completes 12 cycles and does not enter MT, follow-up will begin at the completion of cycle 12.

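### The 6-month minimum for SAE collection in 6.2.4 is undercut by a 30-day adverse-event rule and by follow-up contact that stops at progression

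*Combined protocol and SAP*

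**What the plan says.** **Collection period.** Section 6.2.4 collects all SAEs from the first dose of investigational product to a point after the last dose, given as "minimum of 6 months or until the end of the follow-up period which ever is longer". It adds that "All SAEs regardless of causality will be collected until the end of the follow-up period". An SAE must be reported to the ofatumumab supplier within 24 hours of the investigator being notified.

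**Last scheduled safety assessment.** Footnote 9 of the Schedule of Study Assessments (Section 2): "An additional safety assessment will be done 28 days (+/- 2 days) following the last dose of protocol therapy".

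**General adverse-event rule.** The opening of Section 6 follows all adverse events for 30 days after the last dose in cycle 12, ending sooner if consent is withdrawn or other CLL treatment starts. SAEs are not mentioned as an exception.

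**Follow-up contact.** The Schedule has follow-up rows for later anti-cancer treatment and for survival ("Obtain Follow-Up survival information"). Section 5.4 gives the only interval: patients who complete 12 cycles, have not progressed on therapy and do not go on to maintenance "will be followed every 6 months for survival until disease progression, study closure, withdrawal of consent, or death".

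**Other patients.** Section 5.7 says "Treatment will be discontinued at the occurrence of any of the following events", and its list includes progression and harmful adverse events. For patients who stop during cycles 1 to 12, Section 5.9 says "The subject will then enter the follow-up period unless consent is withdrawn". For maintenance patients, "the follow-up period will begin after discontinuation of lenalidomide in MT". Neither group has a stated interval. Section 5.1, describing the assessment after cycle 3, takes patients with progression off the study.

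**The concern.** The protocol sets a long SAE collection period, but the rules that site staff would work from are shorter. Two of them are explicit rather than merely silent. One ends adverse-event follow-up at 30 days, or at new CLL therapy, without setting SAEs apart. The other ends scheduled contact at progression. A site that followed both exactly would not meet 6.2.4.

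Two things are at stake. The first is complete and even capture of late SAEs. Late events are plausible on the protocol's own account: Section 5.2.2.2 gives a mean ofatumumab half-life of about 14 days (range up to 61.5) and says that the time to lymphocyte recovery has not been determined. The second is overall survival, a secondary endpoint. Section 10.4 censors patients at last follow-up. If contact stops at progression, patients are censored just as their risk of death is likely to rise, which would make the survival curve look too favourable.

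**Working it through.** The plan gives no figure for this point, so there is none to reproduce. The check sets the rules side by side and measures the interval between them.

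**1. Length of the minimum.** Taking a month as 30.4375 days (an assumption), 6 × 30.4375 = 182.6 days.

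**2. Which last dose starts the clock.** Section 6.2.4 counts from investigational product and footnote 9 from protocol therapy. Section 5.2.2.5 uses the first term for ofatumumab, and 6.2.4 sits in the section on reporting to the ofatumumab supplier. Section 6.1.5 uses a form that allows several products. Both readings are therefore worked, for a patient who completes cycle 12.

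- *All protocol therapy.* Both clocks start on the same day and the assessment falls on day 26 to 30.
  - 182.6 − 30 = 152.6 days (83.6%)
  - 182.6 − 26 = 156.6 days (85.8%)
- *Ofatumumab only.* By Table 1 the last infusion is on cycle 12 day 1 and the last lenalidomide dose on about day 28, which is 27 days later. The assessment then falls 27 + 26 = 53 to 27 + 30 = 57 days after ofatumumab.
  - 182.6 − 57 = 125.6 days (68.8%)
  - 182.6 − 53 = 129.6 days (71.0%)

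The range is about 126 to 157 days, or 69% to 86% of the minimum. A patient who stops during cycles 1 to 3 receives methylprednisolone and ofatumumab on the same days, so the upper figures apply under either reading. On the ofatumumab clock, the remainder is below 126 days for anyone whose last lenalidomide dose comes more than 27 days after the last infusion.

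**3. Maintenance patients.** Section 5.8 keeps SAE collection during maintenance (item 7) and requires laboratory tests every four weeks (item 1). For these patients the gap starts only after lenalidomide stops. If the clock runs from ofatumumab, six months or more of maintenance covers the minimum completely.

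**4. The 30-day rule.** Applied to SAEs on the all-therapy clock, it would remove 182.6 − 30 = 152.6 days, and more if other CLL therapy began sooner.

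**5. Progression.** Take a completer not on maintenance who progresses 2 months after the last dose. Under 5.4, survival contact ends at that point. Under 6.2.4, SAEs are still due for 6 − 2 = 4 more months with no scheduled contact. If the first six-monthly contact falls at month 6, any earlier progression removes it. A later death has no scheduled route into the overall survival data.

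**6. Progression during cycles 1 to 12.** Section 5.1 takes patients who have progressed at the cycle 3 assessment off the study, while 5.9 places anyone who stops in cycles 1 to 12 into follow-up. The two sections give different instructions for the same patient.

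**The case against.** The strongest reply is that 6.2.4 is the specific SAE rule and therefore prevails over the general sentence in Section 6. Section 5.8 supports this: it restricts which adverse events are recorded in maintenance (item 5) and separately keeps SAEs (item 7). The 30 days also run from the last cycle 12 dose, so the sentence sets no window for early stoppers. This stands, and 6.2.4 is best read as governing. What remains is that Section 6 lacks the clarifying clause that 5.8 has.

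A reader might infer that after about day 30 a late SAE comes to light only by chance. The documents do not support that. Reporting within 24 hours remains mandatory, Section 9.2.2 has internal monitors review case report forms about every 3 months with verification against medical records, and this is a single-institution study.

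A reader might also infer that no follow-up contact ever asks about SAEs. That cannot be established: the Schedule table is poorly preserved and parts of Section 6 are missing from the available text. Nor are early stoppers or patients leaving maintenance without follow-up. Section 5.9 enters both; what it omits is an interval, which is mostly missing detail.

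Finally, 84% to 86% might be taken as the gap for everyone. It holds only if both clocks start on the same day, and not during maintenance.

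None of these replies removes the stated stop at progression, or the conflict between 5.1 and 5.9.

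**Conclusion.** The point holds in a limited form. The 6-month SAE minimum is not supported by the contact rules, and one of those rules, the stop at progression, can end scheduled contact before the minimum is met. For a cycle 12 completer who does not enter maintenance, about 126 to 157 days of roughly 183 (69% to 86%) lie after the last scheduled safety assessment. That range rests on the 30.4375-day month, on reading the minimum as running from the last dose, and on the two meanings of investigational product. The number of SAEs or deaths that would be missed cannot be derived from the documents.

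The primary endpoint is unaffected, because response is assessed at the end of cycle 3. Overall survival is a descriptive secondary endpoint, so the consequence there is a possibly optimistic curve rather than a wrong test. This should be corrected, but it does not threaten the trial's main conclusion.

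**What to change.** 1. In the opening of Section 6, add: *SAEs follow 6.2.4 and are not ended by the start of other CLL treatment.*
2. In 5.4 and 5.9, replace the stop at progression with six-monthly contact, by telephone if convenient, for survival and SAEs. Apply it to all patients off treatment, including after progression, until study closure, withdrawal of consent or death. Add an SAE item to the Follow-Up column of the Schedule.
3. In 5.1, state that patients with progression are removed from study treatment and enter follow-up.
4. Record the date of any new CLL therapy with each SAE reported in follow-up.

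The 28-day assessment and the maintenance recording rules can stay as they are.

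The cost is a few sentences, one case report form item and some contacts. To reach month 6 there is one contact per patient, so at most 45 at full enrolment, and fewer in practice because some patients already have one. After that there are two per patient-year. Some of the added SAEs will be unrelated to the study drugs, which is why the date of new therapy is needed.
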